4.5.3.2 Vital Signs

Vital signs data will be presented by individual listings with flagging of values outside the normal ranges and flagging of marked abnormalities (Roche Standard- refer output specification). In addition, absolute values and changes from baseline for vital signs data will be summarized. Absolute values and Changes from baseline over time plots will be provided.

Vital signs will include measurements of blood pressure (BP- systolic and diastolic), pulse rate, respiratory rate and body temperature (oral or tympanic).

Blood pressure and pulse measurements will be assessed with a well-calibrated automatic instrument with a digital readout in triplicate. The mean of the triplicate recordings will be used for the time point result.

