Appendix 2-Table 2 DAIDS Pyrexia Severity Grading Scale

Grade	Temperature
1 (mild)	38.0 to < 38.6°C (100.4 to < 101.5°F)
2 (moderate)	≥ 38.6°C to < 39.3 (≥ 101.5 to < 102.7°F)
3 (severe)	≥ 39.3 to < 40°C (≥ 102.7 to < 104°F)
4 (life threatening)	≥ 40°C or ≥ 104°F

If the treatment regimen will include NME(s) that may trigger immune activation (and potentially CRS (cytokine release syndrome), additional AEs and the associated clinical management will be specifically reported into the eCRF by the Investigator: flu-like

symptom specific eCRF page for capturing each of the symptoms experienced, presence of hypotension (requiring fluid or use of vasopressors), and presence of hypoxia (requiring medical intervention). Data from eCRF pages on pyrexia and flu-like symptoms in combination with the data on eCRF pages on hypoxia and hypotension will allow the Sponsor to evaluate the severity of AEs associated with immune activation following specific CRS consensus grading (ASTCT Consensus Grading for Cytokine Release Syndrome. Biol Blood Marrow Transplant, 25; (2019) 625-38).

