TLR7 agonist activates innate and adaptive immune responses, and these mechanisms include induction of type I interferon (IFNα). Safety data from the ongoing Phase 1 studies showed IFN-related flu-like symptoms (headache, pyrexia, chills, myalgia, nausea), mostly of mild intensity; and in some participants, hematological abnormalities (e.g., neutropenia, lymphopenia). During the two clinical studies with RO7020531 (NP39305 and YP39553), all hematological abnormalities were asymptomatic and in most cases reversible within 24 to 48 hours.

TLR7 agonists as a class may have the potential, in a dose-dependent manner, to lead to hypotension and distributive shock due to excessive cytokine release (cytokine release syndrome [CRS])—e.g., IL-1,IL-6,IL-10, IFN-γ, TNF-α etc.—by immune activation. CRS can present with a variety of symptoms, from mild symptoms overlapping with mild flu-like symptoms to severe or life-threatening manifestations. Mild symptoms of CRS include fever, fatigue, headache, rash, arthralgia, and myalgia. More severe cases are characterized by hypotension that requires vasopressor treatment and/or hypoxia that requires medical intervention. They can progress to an uncontrolled systemic inflammatory response with circulatory shock, vascular leakage, disseminated intravascular coagulation, and multi–organ-system failure. Flu-like symptoms were observed during the two clinical studies with RO7020531 (NP39305 and YP39553) at 140 mg to 170 mg single or multiple QOD doses up to 6 weeks. These symptoms overlap with and are not distinguishable from mild cases of CRS.

A12.12 ENHANCED SAFETY MONITORING DURING COMBINATION TREATMENT WITH SIRNA + TLR7 + NUC ARM

Based on the emerging data from Phase 1 studies NP39305 (HV and patient cohorts) and YP39553 (single– and multiple–ascending-dose clinical study in Chinese HVs), it became evident that in all cases of flu-like symptoms, the initial onsets emerged within the initial 3 doses of RO7020531. For this reason, pre-dose laboratory analyses and optional extended in-hospital stay with frequent vital sign monitoring (every 2 to 4 hours) and ECGs (pre-dosing and 6 to 8 hours after dosing at each visit) are scheduled for the initial 3 doses of each combination cycle and guided by emerging AEs as follows:

[figure not shown]

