- On Day 85 and/or Day 253 (first day of each cycle of TLR7 dosing), participants will stay in the clinical unit for 12 hours with an option to stay in the clinic for up to 24 hours (at the Investigator's discretion) in case pyrexia and additional flu-like symptom(s) emerge and do not respond to symptomatic treatment (paracetamol/acetaminophen up to 2 g/day) during the first 12 hours post-combination dosing. For those participants who stay up to 24 hours, an additional 24 hours post-dose laboratory assessment will be done on Day 2 and Day 170, respectively.
- On Day 87 and Day 255 (third day of each cycle of TLR7 dosing), participants will stay in the clinical unit for 8 hours with an option to stay in the clinic for up to 12 hours (at the Investigator's discretion) in case pyrexia and additional flu-like symptom(s) emerged and would not respond to symptomatic treatment (paracetamol/acetaminophen up to 2 g/day) during the first 8 hours postcombination dosing.
- On Day 89 and Day 257 (fifth day of each cycle of TLR7 dosing), participants will stay in the clinical unit for 8 hours with an option to stay in the clinic for up to 12 hours (at the Investigator's discretion) in case pyrexia and additional flu-like symptom(s) emerged during the first 8 hours and would not respond to symptomatic treatment (paracetamol/acetaminophen up to 2 g/day) during the first 8 hours postcombination dosing.

The Sponsor will promptly communicate to the Investigator any change to the proposed enhanced monitoring plan based on emerging data and interim safety evaluations. In case the prolonged hospital stay is not required but participants live far away and may need to be back on the following day, the investigator may decide to allow them to stay at a hotel nearby.

The Sponsor will provide participants a thermometer to use for temperature self-monitoring in case flu-like symptoms and pyrexia emerge. If at any time during the combination cycles (siRNA + TLR7 + NUC) participants experience flu-like symptoms with pyrexia (Grade 2 or above), it will be recommended to call the site and the PI or the medical personnel on site:

- may recommend participants visit the clinic for an unscheduled visit according to the SOA in Appendix 12.
- may recommend symptomatic treatment with paracetamol/ acetaminophen up to 2 g/day.

Appendix 12-Figure 2. Safety Monitoring and RO7020531 Dosing Interruption for Flu-like Symptoms and Cytopenia during Combination Treatment with siRNA + TLR7 + NUC

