- RBR = Research Biosample Repository; RNA = ribonucleic acid; siRNA= short interfering ribonucleic acid; TLR = toll-like receptor; Total HBsAg = post-dissociation of HBsAg/HBsAb complexes/components of HBsAg; VB/VR = virological breakthrough/relapse; UV = unscheduled visit.
- ^a Full physical examination at screening and at the end-of-treatment. Limited symptom-directed physical examination at other visits and as clinically indicated. Height at screening only. Weight at screening, Day 1, and Weeks 13, 25, 37, and 49. Eye examination (including fundoscopy) only at screening.
- ^b Blood pressure, pulse rate, respiratory rate and body temperature obtained at least 5 minutes after participant has been in supine/sitting position. Orthostatic hypotension test only at screening. Vital signs assessments on Days 85 and 253: predose, 2-4 hours, 4-6 hours, 6-8 hours and 8-12 hours; Vital signs assessments on day of the second and third RO7020531 dose of the first cycle, on the first day of those switching to QW dosing, and on the days of the second and third RO7020531 dose in the second cycle: predose, 2-4 hours, 4-6 hours, 6-8 hours (and 8-12 hours optional in case of extended in-clinic stay).
- ^c Historical liver biopsy or transient elastography/ARFI/MR/2D- shear wave elastography [2D-SWE] results obtained within 6 months prior to randomization are also acceptable. During screening transient elastography/ARFI/MR/2D-SWE are acceptable.
- ^d Autoantibodies refer to ANA, AMA, ASMA, and a-TPO.
- ^e Alcohol and drugs of abuse screen to be conducted according to local procedures.
- ^f Pregnancy testing for females of childbearing potential only; serum test at screening, urine test at other visits. If urine test is positive, it must be confirmed by a serum test.
- ⁹ HbA1c should be included in hematology, and is required only at screening.
- h If not collected at Day 1, samples for clinical genotyping and HBV RNA sequencing can be collected at any subsequent time point. The sample for HBV RNA sequencing aims at determining the HBV genotype. The HBV genotype may also be inferred using alternative approaches, such as serovariant determination.
- ⁱ Total HBsAg refers to HBsAg measured post-dissociation of HBsAg/HBsAb complexes/components of HBsAg.
- ^j HBV DNA sequencing will be collected in case of virological breakthrough/relapse, blood sample to be collected up to 6 times.

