4.6 OTHER ANALYSES

4.6.1 Summaries of Conduct of Study

The number of participants who were randomized, discontinued treatment, completed treatment, discontinued study and completed the study (including follow-up period) will be summarized by treatment. Major protocol deviations will be summarized and listed by each treatment arm. Separate listing will be provided for the patients who have met the NUC discontinuation criteria at EOT or follow-up but have not stopped NUC (reluctant to do).

For each participant assessment, the baseline value will be the latest non-missing assessment prior to the first dose administration, this being study Day 1 pre-dose. In the absence of data on study Day 1, the latest non-missing value collected during screening will be used, if such data are not available then the assessment baseline value will be missing for that participant.

4.6.2 Summaries of Treatment Group Comparability/Demographics and Baseline Characteristics

Descriptive statistics will be generated for demographic and baseline disease characteristics including sex, race, ethnicity, origin (for Asian participants only), age, weight, height, body mass index, HBV DNA and HBsAg levels, and HBV history including but not limited to duration of HBV disease, likely route of transmission, HBV genotype, HBeAg status, previous HBV treatments (including incidence of Peg-IFN), and length of time on NUCs.

For NUC treatment duration calculation, if there is a break of treatment of less than 6 months then the duration will be cumulative, if break of treatment is more than 6 months, then the last continuous course of treatment with any nucleos(t)ide products prior to baseline (categorized as <3 years, >=3 to <5 years, >=5 years to <10 years, and >=10 years) will be counted. The effect of this duration covariate will be examined with respect to efficacy, immunogenicity, and antiviral endpoints in separate analyses.

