5.2 APPENDIX 2 ANALYSIS DETAILS SPECIFIC TO TLR7 TREATMENT COMBINATION

TLR7 treatment combination arm specific analysis are listed in this appendix.

Immune Pharmacodynamics Biomarker Analysis: Markers of Humoral and Cellular Response

PD biomarker variables measured are listed in Table 7 below.

Table 7 List of Immune PD biomarker variables

Туре	Variable	Label	Unit
Transcriptional	TLR7	TLR7	delta Ct*
Transcriptional	OAS-1	OAS1	delta Ct*
Transcriptional	MX1	MX1	delta Ct*
Transcriptional	ISG-15	ISG15	delta Ct*
Serum soluble protein (cytokine)	IFN-α	IFN-alpha	ng/L
Serum soluble protein (cytokine)	IFN-γ	IFN-Gamma	ng/L
Serum soluble protein (cytokine)	IP-10	IP-10	ng/L
Serum soluble protein (cytokine)	TNF-α	TNF-alpha	ng/L
Serum soluble protein (cytokine)	IL-6	IL-6	ng/L
Serum soluble protein (cytokine)	IL-1	IL-1	ng/mL
Serum soluble protein (cytokine)	IL-10	IL-10	ng/L

^{*} delta Ct will be provided by the lab performing the analysis.

For each PD variable, descriptive statistics will be presented separately by treatment arm, appropriate TLGs will be produced as listed below.

- 1) Descriptive Statistics- N, Mean, SEM, SD, Median, Min, Max
- Geometric Mean and Change from baseline (baseline for the period) for each time point- tables and plots
- 3) Plot of Absolute Values over Time
- 4) Fold Change (FC) from BL for each time point tables and plots

Cytokine and Neopterin Variables:

Combination Therapies for CHB—F. Hoffmann-La Roche Ltd Statistical Analysis Plan WV41073

- Log10 for each variable at each time point
- Fold change from baseline for each time point based upon raw data
- Log10 fold change from baseline for each time point

Interferon-alpha:

 Systemic Interferon post dose is defined as interferon-alpha post dose > LLOQ pg/mL

Transcriptional Variables:

 Fold change from baseline for each time point calculated as 2**(Change from BL), eg, If change from BL=3 then fold change from baseline = 2**(3) =8.

PD data processing rules-

- Values below limit of quantification set to limit of quantification for cytokine and neopterin derived variables ('<' stripped from string).
- Raw value as transmitted to Roche for cytokine and neopterin variables
- Raw value is negative of original value as transmitted to Roche for transcriptional variables

Relationship between categorical HBsAq and PD Biomarkers:

The primary efficacy parameter is the incidence of HBsAg loss (that is <0.05IU/ml) at 24 weeks post EOT.

HBsAg will be categorized as;

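### Cheap improvement, not an error: in the siRNA + TLR7 + NUC arm the SAP text summarises vital-sign change only from Day 1, although same-day pre-dose readings are taken on the monitored TLR7 dosing days

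*SAP*

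**What the plan says.** **Summary planned.** SAP 4.5.3.2 plans individual listings with flags, plots over time, and that "absolute values and changes from baseline for vital signs data will be summarized". It names no reference other than baseline and, unlike the ECG text in SAP 4.5.3.3, does not say that the tables are split by nominal time.

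**Baseline.** SAP 4.6.1 states that for each participant assessment "the baseline value will be the latest non-missing assessment prior to the first dose administration, this being study Day 1 pre-dose". SAP 4.1 agrees: the last valid value before the first study drug. In this arm the first study drug is siRNA on Day 1.

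**TLR7 dosing and monitoring.** Protocol Appendix 12 gives TLR7 in Weeks 13–24 and 37–48 only. A12.12 explains the close watch on the first three doses of each cycle: "in all cases of flu-like symptoms, the initial onsets emerged within the initial 3 doses of RO7020531". It then sets the stays: "On Day 85 and/or Day 253 (first day of each cycle of TLR7 dosing), participants will stay in the clinical unit for 12 hours", followed by 8-hour stays on Days 87 and 255 and on Days 89 and 257. Appendix 12-Table 4, footnote b, schedules "Vital signs assessments on Days 85 and 253: predose, 2-4 hours, 4-6 hours, 6-8 hours and 8-12 hours". Doses 2 and 3 have a pre-dose reading and three post-dose windows, with 8–12 h optional if the stay is extended.

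**Named risk.** A12.11 warns that "TLR7 agonists as a class may have the potential, in a dose-dependent manner, to lead to hypotension and distributive shock".

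**Period baseline elsewhere.** For the TLR7 immune biomarkers, SAP Appendix 2 (section 5.2) plans "Geometric Mean and Change from baseline (baseline for the period) for each time point- tables and plots".

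**The concern.** The timed readings are there to catch an effect that starts within hours of a TLR7 dose. The natural description of such an effect is each participant's post-dose value minus that day's pre-dose value. The SAP text instead measures every change from a value taken before siRNA, about 12 or 36 weeks earlier. That change mixes the acute response with ordinary between-visit variation, any drift, and any effect of siRNA since Day 1.

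Day 1 does work as a reference where TLR7 itself starts on Day 1, as in the CpAM + TLR7 + NUC arm (Appendix 8). That arm has been terminated. The same rule fits less well in the ongoing arm, where TLR7 is delayed.

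At stake is how clearly tolerability is described in one arm of about 30 participants. The primary endpoint is not involved.

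**Working it through.** The plan gives no figure on this point, so there is none to reproduce.

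**1. Distance from the reference.** Inputs: Day 1 (SAP 4.6.1) and the nominal TLR7 days (Protocol A12.12). Gap = dosing day − 1.

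| Dose | Cycle 1 | Cycle 2 |
|---|---|---|
| 1 | 85 − 1 = 84 days | 253 − 1 = 252 days |
| 2 | 87 − 1 = 86 days | 255 − 1 = 254 days |
| 3 | 89 − 1 = 88 days | 257 − 1 = 256 days |

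Visit windows (Day 85 ±1; Day 253 ±2 or ±3 in different parts of the table) move these by a few days. With the same-day pre-dose value the gap is 0 days.

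**2. What the planned tables can already show.** If they are split by time and the data are complete, the mean acute shift can be recovered:

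mean(post − Day 1) − mean(pre − Day 1) = mean(post) − mean(pre).

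Its spread cannot. The SD of (post − pre) is √(s²post + s²pre − 2·r·s_post·s_pre), and r, the correlation between the two same-day readings, does not appear in any separate summary of each time. Nor does each participant's largest change. Both could be built by hand from the listings.

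**3. Precision.** Assume equal SD σ at each time and correlation ρ between the post-dose value and its reference. Then SD(change) = σ√(2(1 − ρ)), and

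ratio of SDs, same-day to Day 1 = √((1 − ρ_same)/(1 − ρ_Day1)).

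The documents give no correlations. Over an assumed range:

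| | ρ_same 0.6 | ρ_same 0.7 | ρ_same 0.8 |
|---|---|---|---|
| ρ_Day1 0.3 | 0.76 | 0.65 | 0.53 |
| ρ_Day1 0.5 | 0.89 | 0.77 | 0.63 |
| ρ_Day1 0.6 | 1.00 | 0.87 | 0.71 |

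For example, √(0.2/0.7) = 0.53 and √(0.4/0.4) = 1.00. The last entry is the case of no gain.

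**4. A trap in the remedy.** Dose 1 has four post-dose windows; doses 2 and 3 have three plus an optional one. A maximum over more readings is larger by chance alone. With no drug effect, equal means and equal correlation ρ among same-day readings, the mean largest fall is σ√(1 − ρ) × m, where m is the expected maximum of k independent standard normal values (1.029 for k = 4, 0.846 for k = 3). For systolic pressure with an assumed σ of 12 mmHg:

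- ρ = 0.7: 12 × 0.548 = 6.57; four windows 6.8, three windows 5.6; difference 1.2 mmHg.
- ρ = 0.8: 12 × 0.447 = 5.37; four windows 5.5, three windows 4.5; difference 1.0 mmHg.

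So a largest fall tabulated by dose number would make dose 1 look 1.0–1.2 mmHg worse than doses 2 and 3 by artefact.

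**The case against.** The strongest reply is that little is lost. Values outside normal ranges and marked abnormalities are flagged for each participant. Absolute values are summarised and plotted, and the mean within-day shift can usually be worked out. Flu-like symptoms, hypotension and hypoxia have dedicated eCRF capture (Protocol Appendix 2, section 3.1), and symptomatic or clinically significant vital-sign changes are adverse events (Appendix 3, section 5). The interim safety endpoints in SAP 4.7.1 are adverse events and laboratory results, so no planned decision turns on these tables. SAP 4.5.3.2 also refers to an output specification that is not among the documents and might already contain the table.

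Most of this stands. It limits the point to the SAP text and to a descriptive refinement. Two things remain. The dedicated hypotension item covers only hypotension needing fluid or vasopressors, so it would not record a moderate fall. And no planned summary gives the paired spread or the individual maxima.

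A second objection also stands: the gain in precision depends on same-day readings correlating more strongly than readings 12 to 36 weeks apart. That is plausible, but it is an assumption.

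A reader might go further and ask for counts of large pressure falls, or extend the argument to QTcF. The SAP plans no classes of vital-sign change, so such counts would judge the baseline on a statistic that the plan does not use. QT prolongation is not named as a TLR7 risk.

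**Conclusion.** The point holds as an optional improvement. The SAP text measures vital-sign change on the monitored TLR7 days only from a value nominally 84–88 or 252–256 days earlier, while the better reference for an acute effect is already collected. The missing item is a paired summary of within-day change: its SD and the individual maxima. The size of the gain is unknown. Under the assumed correlations and equal SDs, the SD of change would be 0.53–1.00 times as large, where 1.00 means no gain.

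A reader might infer that the Day 1 summary would hide a hypotensive signal, or that the arm is poorly monitored. The documents do not support either. Without drift the mean shift is the same for both references, the listings show individual values, and participants are watched in clinic for 8 to 12 hours. Nor is the period baseline for biomarkers a contradiction within the SAP: it is a choice made for one set of variables that could usefully be made for another.

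**What to change.** In SAP 4.5.3.2, for TLR7 dosing days with timed readings, add change from the same-day pre-dose value in blood pressure, pulse and temperature, by nominal post-dose window, with the number of participants who have both readings. This wording also covers the monitored first dose after a reduction to 100 mg QOD or a switch to QW, which falls on variable days.

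If a maximum fall or rise is shown by dose number and cycle, compute it only over the windows common to all doses (2–4, 4–6 and 6–8 h) and show 8–12 h separately. Keep change from Day 1 as the summary across arms.

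Footnote four limits:

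- siRNA is also given on Days 85 and 253.
- There is no timed control, so time-of-day effects remain.
- Pre-dose values at doses 2 and 3 come about 48 h after a TLR7 dose and may carry over.
- The optional 8–12 h reading at doses 2 and 3 is taken selectively, because the extended stay is triggered by symptoms.

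The cost is a few lines of SAP text, one derived variable per parameter and a few extra descriptive tables. No new data are needed, and the primary endpoint, power and conduct are unchanged.

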4.5.3.3 ECGs

- Summary descriptive statistics for the actual values and changes from baseline will be tabulated by nominal time for HR, QRS duration, PR, QT, QTc interval, QTcF (Fridericia's correction) and RR. Actual values and changes from baseline over time plots will be created for the above ECG parameters.
- For multiple measurements taken at a nominal time point, the average of these
 measurements will be used as the value at that nominal time point in all summaries.
- In addition, QTcF will be categorized at each time point as ≤450 ms, >450 480 ms, >480 500 ms and >500 ms and summarized.
- Similarly, a summary will be provided of the QTcF increase from baseline at each time point categorized as < 30 ms, 30 – 60 ms, and > 60 ms.
- Changes of the overall ECG interpretation, T-wave and U-wave morphology will be summarized.
- Listing of clinically significant ECG abnormalities will be provided
- Abnormal T and U wave will be summarized.

4.6 OTHER ANALYSES

4.6.1 Summaries of Conduct of Study

The number of participants who were randomized, discontinued treatment, completed treatment, discontinued study and completed the study (including follow-up period) will be summarized by treatment. Major protocol deviations will be summarized and listed by each treatment arm. Separate listing will be provided for the patients who have met the NUC discontinuation criteria at EOT or follow-up but have not stopped NUC (reluctant to do).

For each participant assessment, the baseline value will be the latest non-missing assessment prior to the first dose administration, this being study Day 1 pre-dose. In the absence of data on study Day 1, the latest non-missing value collected during screening will be used, if such data are not available then the assessment baseline value will be missing for that participant.

4.6.2 Summaries of Treatment Group Comparability/Demographics and Baseline Characteristics

Descriptive statistics will be generated for demographic and baseline disease characteristics including sex, race, ethnicity, origin (for Asian participants only), age, weight, height, body mass index, HBV DNA and HBsAg levels, and HBV history including but not limited to duration of HBV disease, likely route of transmission, HBV genotype, HBeAg status, previous HBV treatments (including incidence of Peg-IFN), and length of time on NUCs.

For NUC treatment duration calculation, if there is a break of treatment of less than 6 months then the duration will be cumulative, if break of treatment is more than 6 months, then the last continuous course of treatment with any nucleos(t)ide products prior to baseline (categorized as <3 years, >=3 to <5 years, >=5 years to <10 years, and >=10 years) will be counted. The effect of this duration covariate will be examined with respect to efficacy, immunogenicity, and antiviral endpoints in separate analyses.

